- b. Participants will need to sign consent (caregivers) and assent (youth) forms. Following enrollment, youth and caregivers will be given a baseline assessment consisting of a series of questionnaires. Both youth and caregivers assigned to the MCI + IPT-A group will attend one or two MCI sessions lasting approximately 45 minutes. The youth participants will continue to receive IPT-A for 12 sessions and will be given additional assessment questionnaires at weeks 4, 8, and 12. Youth in the IPT-A only group will begin IPT-A sessions immediately following enrollment and will follow the same assessment schedule. Assessments, screenings, and MCI and IPT-A sessions will be conducted at the youth's school.
- c. The MCI coupled with the IPT-A will consist of 13-15 intervention sessions. The IPT-A alone will consist of 12-15 intervention sessions. The MCI will occur with parents or legal guardians and students for one hour (60-75 minutes) over 1-2 sessions (Note: the screening and initial assessment will occur prior to the MCI session). The remaining 12-15 sessions will focus on the delivery of the evidence-based depression treatment, IPT-A, which will occur in weekly 30-45 minute individual therapy sessions (over 12 weeks, additional if a week is skipped) with the students and allowing possible concurrent sessions with the parent or legal guardian as needed. Thus, the intervention should last for approximately 3-4 months.

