- d. A member of the research staff will conduct interviews and assessments. SMH clinicians will deliver the MCI and IPT-A interventions. This study will feature a 2-group randomized design. Eligible students will be randomized to receive the MCI and IPT-A enhanced intervention, or to receive IPT-A only. Astor Services for Children & Families is a community based, non-profit organization that provides children's mental health services, child welfare services, and early childhood development programs. Astor serves children and families in the Bronx through school-based mental health clinics. These on-site mental health clinics, which are all licensed mental health clinics in New York State, offer individual, group, and family treatment, as well as crisis intervention on school campuses. Six to eight clinicians employed by Astor will deliver both the MCI and IPT-A interventions, or the IPT-A alone. Therefore, Astor Services for Children & Families will be responsible for administering individual psychotherapy at their 6 selected school-based sites in the Bronx, but will not be involved in the design, oversight and/or management of the study.
- e. Screening tools will be distributed to students in a take-home packet, completed along with a consent form, and collected by research staff or SMH clinicians. Assessment questionnaires will be given by a member of the research staff and delivered to the research coordinator when completed.

Incentives

Incentives will be provided to both youth and caregiver participants in the form of gift cards. If participants withdraw prior to study completion, they may keep any gift cards they received but will not receive additional gift cards that would have been distributed at a later point in the study. Participating caregivers receive a \$20 gift card at baseline, \$15 gift card following the post-MCI assessment, and then a \$15 gift card following the assessments at week 4, week 8 and week 12. Youth receive a \$15 gift card at baseline, \$10 gift card following the post-MCI assessment, \$10 gift card following the week 4 assessment, \$10 gift card following the week 8 assessment, and then a \$10 gift card following the week 12 assessment. The total gift card amount for caregivers completing the study is \$80 in gift cards; the total for youth participants completing the study is \$55 in gift cards.

Participant Identification, Recruitment, & Selection

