All student participants will require parental consent and student assent to participate in the study. At each school, students will be recruited through a school-wide screening process. Prior to screening, the research team will hold an informational meeting for parents, adolescents, and teachers regarding adolescent depression, rationale for screening for elevated depression, and treatment options including the current study. Parents will then be sent a PHQ-9 and a consent form for their child's participation in the screening (students will take home in a packet) as part of usual care procedures at the participating NYC DOE schools. Upon receipt of a willingness to be contacted form, the research team will contact families about their interest in participating in the study. Upon an expressed interest, a research team member will meet the family to explain the study and cover the informed consent procedures (and child assent). The research team member will explain the study to the family, including the randomization procedure. They will understand that they are participating in a research study and that participation is voluntary. The consents also give information regarding what the study entails, incentives, and requirements of participants. Students and parents or legal guardians will also be given a copy of all consents/assents signed for their records and are welcome to contact any member of the research staff or the school mental health clinicians regarding questions or concerns they may have. Participants may choose not to participate. Consents will be written at the 7th grade reading level for parents or legal guardians and at the 5th grade level for student assents. The research team member will be sure that the participants understand all aspects of the consent process. Note: For those families who do not wish to participate in the study, usual care treatment will be offered. With informed consent and child assent obtained, the research team member will administer the CES-D screen. If the student scores above the clinical cutoff on the CES-D (i.e., 16 or higher), and the Hamilton (i.e., 10 or higher), and meet other inclusion/exclusion criteria, the student will be enrolled. We anticipate these procedures will be completed at the participating schools.

Participation Consideration

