depressive symptoms. For example, as a standard of practice in the IPT-A treatment, SMH clinicians assess current symptom levels at the beginning of each session. Further, SMH clinicians complete the Children's Global Assessment Scale (C-GAS) to assess for global impairment associated with mood disorder. Additionally, the Hamilton Rating Scale for Depression (HRSD) and Center for Epidemiological Studies-Depression Scale (CES-D) are administered at baseline, post-MCI session, and at weeks 4, 8 and 12. If at any time the symptoms, as indicated by the HRSD and CES-D, reach a clinically severe level (HRSD score of 28 or greater; CES-D score of 31 or greater), the PI and SMH clinicians immediately ask follow-up questions to determine whether the youth is expressing suicidal ideation; if suicidal ideation was indicated, the PI and SMH clinicians further assess whether the youth has a plan, whether there is access and means to follow through with a plan, the level of suicidal intent and the presence of current suicidal gestures. We also contact the caregiver and provided information about emergency psychiatric services for determination of whether hospitalization is necessary. If there was a pattern of worsening depressive symptoms or de-compensation in the absence of suicidal intent during the course of the study (as measured by the Clinical Global Impressions (CGI), which was given weekly by the SMH clinician and indicated by a 6 or 7 on the CGI for 2 consecutive weeks), the PI in consultation with the SMH clinicians will make a determination of whether the youth is: (1) appropriate for the study; or (2) in need of more emergent psychiatric care such as hospitalization. Referral may also be made back to a primary care physician or to community-based mental health services in instances where participants might worsen during the course of the study. Again, guidance on this determination is informed on a session-by-session basis (e.g. symptom query is a standard practice of the IPT-A treatment) and via the standardized assessments of depression (e.g. HRSD and CES-D). If hospitalization was necessary, information on psychiatric services (e.g. hospitalization) will be provided to the caregiver.

Benefits of the Study

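### Does the extra post-MCI assessment, with no date for controls and no stated week 0, leave the two arms on conflicting schedules?

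*Protocol*

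**What the plan says.** Three places in the protocol bear on the schedule.

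- **Description of study procedures, item b.** Youth and caregivers have a baseline assessment. Then "Both youth and caregivers assigned to the MCI + IPT-A group will attend one or two MCI sessions", and after that "The youth participants will continue to receive IPT-A for 12 sessions and will be given additional assessment questionnaires at weeks 4, 8, and 12". For controls: "Youth in the IPT-A only group will begin IPT-A sessions immediately following enrollment and will follow the same assessment schedule". No post-MCI assessment is mentioned, and no instrument is named.
- **Incentives.** Cards are paid at baseline, then a "gift card following the post-MCI assessment", then at weeks 4, 8 and 12, for caregivers and for youth. One completer total is given for each: 80 dollars for caregivers and 55 dollars for youth. Neither the cards nor the totals are split by arm.
- **Risks of the Study.** The HRSD and CES-D "are administered at baseline, post-MCI session, and at weeks 4, 8 and 12", again without restriction to one arm.

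Item c adds that IPT-A is given in weekly sessions over 12 weeks, with extra weeks if one is skipped. The Informed Consent section notes of the consent forms: "The consents also give information regarding what the study entails, incentives, and requirements of participants". Those forms are not in the public file. The SAP sets out no visit schedule.

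**The concern.** Item b gives three follow-ups to both arms; the other two sections give four. An assessment named after the MCI has no obvious date for a youth who never has an MCI session. A reader could therefore ask whether controls have it at all. If they do not, the single completer totals would be wrong for the control half of the sample.

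The second worry is the start of the week count. Controls begin IPT-A straight after enrollment, while the other arm has one or two MCI sessions first. Counted from enrollment, the MCI arm would have had less IPT-A than controls at each visit. Counted from the first IPT-A session, the MCI arm would be assessed later after baseline. Either way the arms could differ slightly in what a given visit represents.

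There is also a safety angle, because the HRSD and CES-D scores set off further questioning: "If at any time the symptoms, as indicated by the HRSD and CES-D, reach a clinically severe level". A missed assessment would be one fewer chance to detect this.

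**Working it through.** **Gift card totals (Incentives section).**

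- Caregivers, with the post-MCI card: 20 + 15 + 3 × 15 = 80 dollars. This reproduces the stated total. Without it: 20 + 3 × 15 = 65 dollars.
- Youth, with the post-MCI card: 15 + 10 + 3 × 10 = 55 dollars. This reproduces the stated total. Without it: 15 + 3 × 10 = 45 dollars.

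The totals fit baseline plus four follow-ups and nothing shorter. Since each is stated once for all completers, the plain reading is that both arms have the fourth assessment.

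**Is item b a complete list?** It mentions the week 4, 8 and 12 questionnaires for youth only, yet the Incentives section pays caregivers at those same weeks. So item b already leaves out assessments that the protocol clearly intends. It names weeks 4, 8 and 12 in the sentence about IPT-A, and in the MCI arm a post-MCI assessment would come before that phase. It nowhere says that these are the only follow-ups.

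**Do staff have two instructions for the HRSD and CES-D?** No. Item b names no scale. The Risks of the Study section holds the only follow-up schedule for these two scales, and it includes the post-MCI time point.

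**Week 0.** Assume weekly sessions, no skipped week, and an MCI lasting m weeks. The documents give no value for m; take 0 to 2.

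| Anchor | m = 0 | m = 1 | m = 2 | Controls |
|---|---|---|---|---|
| Enrollment: IPT-A sessions by weeks 4/8/12 (w − m) | 4/8/12 | 3/7/11 | 2/6/10 | 4/8/12 |
| First IPT-A session: week 12 in weeks after enrollment (12 + m) | 12 | 13 | 14 | 12 |

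Under the enrollment anchor, the MCI arm has had 1/12 = 8.3% (m = 1) or 2/12 = 16.7% (m = 2) fewer IPT-A sessions at week 12. Under the IPT-A anchor, session counts are equal and the last visit falls one or two weeks later. If the MCI and the first IPT-A session share a week, both differences vanish. Item b puts 12 IPT-A sessions and weeks 4, 8 and 12 in one sentence, and item c spreads weekly IPT-A over 12 weeks. Both point to the first IPT-A session as week 0, so the 8 to 17% shortfall needs the less likely anchor together with an MCI duration that the documents do not give.

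**Power.** The SAP's figures use 30 per arm, two-sided alpha 0.05, power 0.80 and a pre-post correlation of 0.65. The detectable difference from a t test with 30 per arm is d = 0.736, against the SAP's 0.75. With baseline adjustment it is 0.736 × √(1 − 0.65²) = 0.736 × 0.760 = 0.56, against the SAP's figure of about 0.55. Neither calculation uses the number of visits or the week anchor.

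**The case for a change.** The best case for a change runs as follows. Item b is the part of the protocol that assigns the control schedule, and it omits the visit. No section gives controls a date for it. A control visit matched in time could fall after IPT-A has begun, while the MCI arm's falls before, so the two would not measure the same thing. If controls do not have the visit, their totals should read 65 and 45 dollars. One schedule table would settle all of this at almost no cost and would add no visits.

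Part of this stands. The control date is not written down, week 0 is not defined in words, and anyone comparing the arms on the post-MCI measure would need to know when controls were assessed. The rest is weaker:

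- The 65 and 45 dollar totals arise only under the reading that the Incentives section does not support.
- The consent forms, which may tell families the schedule, are not available here and cannot be counted as missing.
- Item d has research staff, not each school's clinicians, carry out the assessments, so there is no sign of six schools improvising.
- The safety consequence is limited by the symptom check at each IPT-A session and the weekly CGI, both described under Risks of the Study.
- Skipped weeks, which item c expects, will make the number of sessions received by week 12 vary within both arms whichever anchor is used.

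**Conclusion.** The concern is right that the listings differ (three follow-ups against four) and that two details are unwritten: when controls have the assessment equivalent to the post-MCI one, and from which day the weeks are counted. It does not amount to a contradiction that calls for a change. The fuller lists agree with each other, the stated totals of 80 and 55 dollars confirm four follow-ups for every completer, and the wording on IPT-A sessions points to the first of these as week 0.

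The size is small. At most, the arms differ by one or two weeks in IPT-A received or in time since baseline, assuming weekly sessions and an MCI of one or two weeks; the difference may be nil. No stated sample size, detectable effect, threshold or conclusion becomes wrong if the plan is followed as written. The conclusion rests on reading the unrestricted wording of the Incentives and Risks of the Study sections as covering both arms. If that reading were mistaken, the effect would be control-arm card totals overstated by 15 dollars (caregivers) and 10 dollars (youth), still with no bearing on the planned comparisons at weeks common to both arms. This is missing detail that a study team would settle in its visit calendar.

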1 R34 MH119290-01

Version date 4/17/2019

Summary of the Research

The overall goal of this study is to examine the effectiveness of the Making Connections Intervention, hereafter referred to as the MCI. Based on the Unified Theory of Behavior and Stages of Change Theory, the MCI is designed to facilitate adolescents' identification of perceptual and actual barriers that influence their mental health treatment acceptability (i.e. engagement, perceived relevance, and satisfaction), and equip them with the skills to overcome these barriers at the initiation and/or during the course of treatment. As a test of the MCI, our target population was urban, Black adolescents screened for depression and referred for Interpersonal Psychotherapy for Depressed Adolescents, or IPT-A, for treatment. Prior research by the PI indicates that depressed, Black adolescents are likely to have untreated depression due to negative family influences, negative perceptions of services and providers, or self-stigma associated with experiencing depressive symptoms. This is of public health significance because: (1) this group uses less mental health services than any other adolescent group, and non-financial factors (e.g. mental illness stigma, negative perception of providers/services) plays a significant role in their lower service use; (2) if/when they do enter treatment, low engagement and early termination typify their experiences; and (3) suicide, a byproduct of untreated depression, has increased among this group, narrowing the gap in suicide rates between White and Black adolescents. To date, limited work has been done to improve treatment acceptability among urban, Black adolescents with depression, especially those in their middle-school age years. This study proposes a small-scale trial in New York City DOE school-based mental health clinics throughout the Bronx, where Black youth would be randomized to receive the MCI+IPT-A or IPT-A alone.

Project Information II

Description of study procedures:

- a. The study will be conducted at six (6) New York City Department of Education (DOE) Middle and High School School-Based Mental Health Clinics.

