We based our sample projections on the demographic data from our partnering NYC DOE schools. The schools we are partnering with have approximately similar percentages of male and female students, of whom over 20% are African American. The students who attend these schools are generally from low-income families (live below the poverty line, receive Medicaid). We will enroll a total of 60 subject and randomly assign them to the MCI + IPT-A or IPT-A only in a 1:1 ratio. Based on screening rates in our previous R21, we anticipate recruiting 60 adolescents (10 per school-based site). In our R21 study, we were able to recruit 24 adolescent/parent pairs from our partnering schools using similar screening processes.

At each school, students with elevated depression will be identified through a school-wide screening process. We will work in concert with NYC DOE school mental health (SMH) staff to screen participants as per usual care procedures. We will identify participants through the following procedures. First, a screening (PHQ-9) and consent form (caregivers provide permission for their child to be seen in SMH services) are sent home with all students at the beginning of the academic year. We have requested (per IRB approval) to also send home a

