permission to be contacted form, along with a letter describing our study. If caregivers agree to be contacted, the SMH staff will share with the research staff the contact information of students who scoring above the clinical cutoff of 11 (range 0 to 27). Astor Services for Children & Families used the school-wide screening method with the Strengths and Difficulties Questionnaire in 2015 and had an approximately 50% return rate on the screenings/consent forms. Research staff will not receive names of students whose parents do not provide a permission to be contacted form. Of the received forms, the research staff will contact the family to set up a time to consent/assent for the study and screen the adolescent using our standard screening procedure, which is to administer the Center for Epidemiologic Studies Depression Scale (CES-D). Second way we also will recruit participants is that using another standard of care in SMH service delivery, which is to recruit through the school-based clinics among those students presenting to services for mental health needs. That is, SMH staff at the participating schools currently receive referrals from NYC DOE social workers, guidance counselors, administrators, teachers, other school-based providers, family members, and self-referrals. All referrals are screened using the PHQ-9. Upon receipt of referrals, the SMH staff person will share a brochure of the study and a letter to be shared with the family, along with a permission to be contacted form. Following assessment, [name] and [name] will review assessment, establish eligibility, and follow random assignment procedures. Randomization lists will be prepared by [name] who will have no contact with participants, clinicians, or study staff members. We will randomize within schools and provide clinicians information per each case about whether the participant will receive the MCI + IPT-A or IPT-A only. Clinicians will complete fidelity assessments, and we will randomly listen to audiotapes of sessions to document the extent of contamination or the potential of it. We will also make sure to discuss instances of contamination (or the potential of it) during weekly supervision with the clinicians. Note: We will keep track of the % of families who return the permission to be contacted forms. Research staff will follow-up on all returned forms and schedule a time to consent/assent for the study and screen the adolescent using our standard screening procedure

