**Engaging Black Youth in Depression and Suicide Prevention Treatment Within Urban Schools**

**1 R34 MH119290-01**

**06/28/2021**

**NCT03940508**

## Statistical Design and Power

With a sample size of only 30 per condition (total  $N = 60$ ), power is a challenge. For a traditional single degree of freedom contrast of means, assuming an alpha level of 0.05 for a two tailed test and power of 0.80, the effect size sensitivity corresponds to a population Cohen's  $d$  of 0.75, which represents about 12% explained variance. This represents sensitivity to a large effect. For a correlation coefficient,  $N = 60$  and using the same general power parameters as above, the effect size sensitivity corresponds to a population correlation of 0.35, or, again, about 12% explained variance.

Approaches to increasing statistical power generally focus on increasing sample size, but an alternative strategy is to introduce covariates that reduce within-condition error. This approach leads to a more sensitive significance test for the treatment effect. In the proposed R34, we will increase the statistical power by adjusting for relevant covariates measured at baseline. Covariate adjustment for a pretreatment score on each outcome measure will substantially increase statistical power. For example, if pretreatment and post treatment scores correlate  $r=.65$  (which seems reasonable based on our prior research, then the effect size sensitivity for an  $N$  of 30 per group and power of 0.80 corresponds to a Cohen's  $d$  of about 0.55. Importantly, as we explore power and as a function of baseline and other covariates, we can make more informed sample size decisions for the larger R01. In general, the robust methods of analysis will be as powerful or more powerful than the least squares methods, so the power estimates above apply, conservatively, to the robust methods as well.

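### School is the randomisation stratum but is not named in the SAP's covariate strategy; a random school intercept would recover some power if schools differ

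*Protocol*

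**What the plan says.** **Protocol, Participant Identification, Recruitment, & Selection.** The plan is to enrol 60 youth, about 10 per site, and "randomly assign them to the MCI + IPT-A or IPT-A only in a 1:1 ratio". Allocation is stratified: "We will randomize within schools and provide clinicians information per each case". Block size is not given.

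**Protocol, Description of study procedures.** The six sites are "Middle and High School School-Based Mental Health Clinics". On delivery: "Six to eight clinicians employed by Astor will deliver both the MCI and IPT-A interventions", or IPT-A alone. Whether each clinician works at a single site is not stated.

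**SAP, Statistical Design and Power.** Detectable effects at 80% power are d = 0.75 for a simple contrast of means and about 0.55 after adjusting for a baseline score correlated .65 with the outcome. The strategy is "we will increase the statistical power by adjusting for relevant covariates measured at baseline", and the only covariate named is the pretreatment score: "Covariate adjustment for a pretreatment score on each outcome measure will substantially increase statistical power". The SAP also says that "the robust methods of analysis will be as powerful or more powerful than the least squares methods", without naming those methods. Neither document names school as a covariate, stratum or random effect in the analysis, and neither gives a between-school variance.

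**The concern.** The SAP treats limited power as its main difficulty and covariate adjustment as the remedy. School is known for every youth, cannot be missing, and is already built into the randomisation, yet it is not on the stated list.

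If the lists are balanced within school, the arm difference is largely free of between-school variance. A model without school still leaves that variance in its error term, so the standard error is too wide when schools differ. If the lists are not blocked, the standard error is right, but the estimate carries chance school imbalance that a school term would remove. In both cases the estimate is unbiased. What is at stake is precision and, with balanced lists, a test that rejects less often than its nominal 5%.

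The documents give some reason to expect differences: middle and high schools are mixed, and different clinicians may serve different sites. If each clinician works at one site, a school term would also absorb most clinician differences.

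**Working it through.** **Inputs.** From the documents: 30 per arm, two-sided alpha 0.05, power 0.80, r = .65, d = 0.75 and 0.55, six schools of about 10, 1:1 within school. Assumed: the ICC, meaning school's share of the outcome variance left after baseline, at 0, .05, .10 and .20.

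**1. The SAP's own figures.**
- Unadjusted: d = 0.75 gives 81.5% power by the t-test (58 df); the detectable d at 80% is 0.736.
- Adjusted: residual SD = √(1 − .65²) = 0.760; SE = 0.760 × √(2/30) = 0.196; 0.55/0.196 = 2.80. The normal formula gives 80.0% power and the noncentral t (57 df) 78.7%, with a detectable d of 0.559.

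Both stated figures reproduce to within 2 points of 80%.

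**2. Standard error with and without school (5:5 in each of six schools).** Arm is then orthogonal to school. Take total residual variance as 1, with ICC = ρ.
- True variance factor of the arm difference: 1 − ρ.
- Expected error variance when school is omitted: (50ρ + 58(1 − ρ))/58 = 0.862ρ + (1 − ρ).

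At ρ = .20 the true SE is 0.196 × √0.80 = 0.175, and the model without school reports about 0.196 × √0.972 = 0.193. Simulation with the baseline slope estimated gives 0.178 and 0.194, a ratio of 0.92. Type I error without school is 4.8/4.7/4.0/3.3% at ICC 0/.05/.10/.20; a separate run gave about 3.5% at .20.

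**3. Power at d = 0.55, r = .65, N = 60.** There were 20,000 simulated trials per cell, with Monte Carlo SE about 0.3 points. The random intercept was fitted by REML and tested with t on 52 df.

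| ICC | Blocked: no school | Blocked: random intercept | Gain | Unblocked: no school | Unblocked: random intercept | Gain |
|---|---|---|---|---|---|---|
| 0 | 78.1 | 78.6 | +0.5 | 77.0 | 77.1 | +0.1 |
| .05 | 78.8 | 80.3 | +1.5 | 76.9 | 77.6 | +0.7 |
| .10 | 79.3 | 82.0 | +2.7 | 78.3 | 80.0 | +1.7 |
| .20 | 81.1 | 86.1 | +5.0 | 78.5 | 83.7 | +5.2 |

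At ICC .02, separate runs with blocked lists gained 0.4 to 1.0 point; with unblocked lists, 0.2. Blocks of 4 in unequal schools (4, 6, 8, 10, 14, 18) gave gains of 0.5, 1.5, 2.3 and 4.8. An outcome with no baseline score (d = 0.74, blocked) gave 0.5, 1.5, 2.5 and 4.8.

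**4. Five school indicators instead.**
- Blocked: 77.8/79.7/81.8/86.1%, so −0.3, +0.9, +2.5 and +5.0 against no school.
- Unblocked: 72.8/74.6/77.8/82.2%, so −4.2, −2.3, −0.5 and +3.7.
- Blocked with an assumed 25% of outcomes missing at random: 63.4 → 61.8% at ICC 0 and 65.8 → 65.7% at .05. A second run gave 64.4 → 63.1% at ICC 0 and no gain at .05. The random intercept lost no meaningful power in this setting.

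**5. Robust estimation.** The SAP names no estimator, so Huber regression serves only as an illustration. Blocked, no school against random intercept: 76.0/76.5/77.0/78.3% against 76.5/78.5/79.6/84.3%. The pattern is the same.

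**6. Test size of the random intercept.** Type I error was 4.9 to 5.4% with t on 52 df and 5.4 to 6.0% with a normal reference. The Huber version gave 5.0 to 5.7%.

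All runs use one post-baseline score, because the documents name no primary time point.

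**The case against.** **The SAP does not exclude school.** Its text is a design and power section, not a full model specification, and its covariate wording is open enough to include school. This stands. The point is that school is not named, and naming it in advance removes a choice made after seeing data.

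**Schools may hardly differ.** The protocol describes a similar sex mix and generally low-income students across the schools. One agency provides treatment at every site, all sites are in one borough, and common severity thresholds apply at entry. The relevant ICC is also what is left after baseline adjustment. This stands: nothing in the documents supports .20 in particular.

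**Part of the small gain is not recovered variance.** The random intercept gains 0.5 points with blocked lists even at ICC 0, where there is nothing to recover; a slightly looser test is the likely reason. This stands, and is why about 1 to 1.5 points is the fair figure at .05.

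**Stronger readings a reader might infer.**
- *That ignoring school inflates false positives, as in a cluster-randomised trial.* It does not. Youth are randomised individually within school, so omission is conservative with balanced lists and correctly sized with unblocked ones.
- *That the trial has less power than the SAP claims.* With blocked lists, power without school does not fall as the ICC rises (78.1% at 0, 81.1% at .20). With unblocked lists it stays at about 77 to 78%.
- *That 5 points are there for the taking.* That figure belongs to an assumed ICC of .20.
- *That any school term will do.* Indicators can lose power with unblocked lists or missing outcomes, and the protocol (Participation Consideration) lets participants withdraw at any time.

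**Conclusion.** The point holds as a minor efficiency matter. The randomisation stratum is not named in a covariate strategy whose stated purpose is to gain power. There is no bias, and the SAP's detectable effects stand.

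With blocked lists the forgone power is about 0 to 1 point at ICC 0 to .02, 1 to 1.5 at .05, 2 to 3 at .10 and about 5 at .20. With unblocked lists it is smaller at .05 and .10 and about the same at .20. With balanced lists and ICC .20, the test without school runs at about 3.3 to 3.5% rather than 5%.

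These sizes rest on an assumed ICC, an unstated block size, a single post-baseline score and, except for the missing-outcome runs, complete data on 60 youth.

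**What to change.** Add one sentence to the SAP: the model for each outcome contains arm, school as a random intercept, and the baseline score where one exists, tested with a t reference (about 52 df with complete data) or a small-sample correction rather than a normal one. Carry the same term into whatever robust estimator is used. Do not offer five school indicators as an equal choice: they cost about 4 points at ICC 0 with unblocked lists, and about 1 to 1.5 points at ICC 0 with no gain at .05 if about a quarter of outcomes are missing, even with blocked lists.

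No new data or design change is needed. The downside is type I error of roughly 5 to 5.5% for the random intercept, since six schools are few. A side benefit is a school variance estimate, imprecise with six schools, for the sample size work that the SAP foresees for the larger trial.
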